## 10.3 HANDLING OF PATIENT TEMPORARY OR PERMANENT TREATMENT DISCONTINUATION AND OF PATIENT STUDY DISCONTINUATION

The IMP should be continued whenever possible. In case the IMP is stopped, it should be determined whether the stop can be made temporarily; permanent IMP discontinuation should be a last resort. Any IMP discontinuation should be fully documented in the e-CRF. In any case, the patient should remain in the study as long as possible.

### 10.3.1 Permanent treatment discontinuation with investigational medicinal product(s)

Permanent treatment discontinuation is any treatment discontinuation associated with the definitive decision from the Investigator or the patient not to re-expose the patient to the IMP at any time.

Patients who discontinue treatment permanently during the treatment period will be assessed as soon as possible using all procedures normally planned for the End-of-treatment Visit with the exception of CT Scan. Patients who discontinue early during the post-treatment period will be assessed as soon as possible using all procedures normally planned for the end-of-study (EOS) Visit.

For patients in whom the surgery date is scheduled after the planned end of study, a follow up contact(s) should be performed around the time of planned surgery to document the surgery date. Surgery data will be collected only until e-CRF Closure and EOS will not be delayed.

Patients will also be instructed to:

- Return to the study site for evaluations of NPS, SNOT-22, at:
  - Week 24, Week 52: If the ETD visit occurred between Week 0-Week 16,
  - Week 52: If the ETD visit occurred between >Week 16-Week 40,
  - Week 64 (EOS): If the ETD visit occurred between >Week 40-Week 52.
- Return and have a CT Scan performed as scheduled at Week 24 and 52.

Patients who discontinue prior to week 40 will have the following assessed through week 52, patients who discontinue after week 40 will have the following assessed through week 64:

- Perform PK and ADA sampling at the initially scheduled visits for these assessments
- Continue to complete the e-diary for nasal congestion, loss of smell daily symptom and anterior/posterior rhinorrhea evaluation
- Continue on MFNS stable dose but patients are not required to complete the INCS use daily in the e-diary after ETD.
- Advise patients with comorbid atopic conditions (such as asthma) not to adjust their treatment without consultation with their physicians.
- Report any AE up to the last scheduled visit (Week 52 or Week 64 depending on the discontinuation date).
- Contact the Investigator during the post treatment period up to the EOS visit if the symptoms worsen requiring medical attention.
  - The Investigator will record in the corresponding e-CRF pages rescue medication prescribed or surgical interventions during the planned study treatment period. Use of oral steroids for rescue treatment of worsening nasal polyps or for another reason will be captured by the Investigator (or designee) on the appropriate page(s) of the e-CRF page and the date and dosing information (daily dose, duration, INN) will be informed. Details on planned date for surgery, type, and outcome (whenever possible) of surgery will be recorded in a specific e-CRF page. If surgery is performed during the study treatment period or follow-up an AE or SAE page will be completed.

For patients undergoing surgery for NP, refer to [Section 9.2.1.5](#) for details.

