STUDY DESIGN	
General design
 
Multinational, multicenter, randomized, double-blind, placebo-controlled, parallel group study comparing the efficacy of dupilumab compared to placebo, in patients with bilateral NP treated with intranasal corticosteroids (INCS).
 
Study periods
 
The clinical trial consists of 3 periods:
 
Run-in period (4 weeks +/-3 days):
 
All patients will enter a run-in period of 4 weeks receiving MFNS of 2 actuations (50 µg/actuation) in each nostril twice daily (BID), total daily dose of 400 µg, starting at Visit 1 (V1), unless the patients are unable to tolerate or there is a specific regulatory requirement preventing use of this dose in which case, they can stay on a lower dose regimen (200 µg once daily) of MFNS.
 
Randomized treatment period (up to 52 weeks +/-3 days):
 
Patients will be randomized to one of the following treatments:
 

• Arm A: dupilumab 300 mg subcutaneous (SC) q2w until Week 52.

• Arm B: dupilumab 300 mg SC q2w until Week 24, then 300 mg q4w until Week 52.

• Arm C: placebo matching dupilumab SC q2w administration until Week 52.

 
All patients will continue on the stable dose of MFNS used during the run-in period except if dose is changed due to adverse event (AE).
 
Rescue:
 
During the study treatment period and off treatment follow-up, based on clinical evaluation, in case of worsening of signs and/or symptoms requiring medical intervention, the Investigator may consider rescue treatment with:
 

• Nasal lavage with saline and/or systemic antibiotics (up to 2 weeks in case of acute infection)

• Short course oral corticosteroids (OCS) (prednisone or prednisolone)

• Sino-nasal surgery for nasal polyps (based on previous observations, 8 weeks of IMP treatment is recommended prior to surgery to allow onset of treatment effect).

 
Patients receiving rescue treatment other than surgery during the study should continue on study drug unless the Investigator decides to withdraw the study treatment (see Section 8.2.2). Before starting treatment with SCS patients should come to the study site for the clinical assessments including endoscopy and PROs.
 
For patients who undergo or are planned for surgery for NP the Investigator may decide to continue IMP up to the time of surgery or end of treatment whichever date comes first (see Section 9.2.1.5 for details). At the time of surgery patients will be permanently discontinued from study treatment and assessed as soon as possible using the procedures described in Section 10.3.1.
 
Post treatment period (12 weeks +/- 3 days):
 
After completing 52 weeks of treatment with the investigational medicinal product (IMP) (or following early discontinuation of IMP or discontinuation from the study), patients will be instructed to:
 
Return to the study site for such evaluations as pharmacokinetic (PK) and ADA, physical examination, nasal peak inspiratory flow (NPIF), University of Pennsylvania Smell Identification Test (UPSIT), NPS, PROs (SNOT-22, VAS),

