#### **10.1.14 Visit 10 (Week 52): End of treatment**

- PRO Patient administration in the e-diary:
  - Daily symptoms of NC, loss of smell and anterior and posterior rhinorrhea,
  - SNOT-22,
  - VAS for rhinosinusitis,
  - Reduced sense of taste symptom severity score,
  - QoL (EQ-5D),
  - ACQ-6 (for patients with asthma).

- Health care resource utilization via e-CRF.
- Inquire about AEs/SAEs and background therapy tolerability.
- Collect IMP and NIMP boxes
- Record all medication use with start date and dose in the e-CRF.
  - Check for use of prohibited medications,
  - Complete rescue medication/surgery page (s) of e-CRF. Use of oral steroids for rescue treatment of worsening nasal polyps or for another reason will be captured by the Investigator (or designee) on the appropriate page(s) of the e-CRF page and the date and dosing information (daily dose, duration, INN) will be informed. Details on planned date for surgery, type, and outcome (whenever possible) of surgery will be recorded in a specific e-CRF page. If surgery is performed during the study treatment period or follow-up an AE or SAE page will be completed.
- Call IVRS/IWRS to register visit and obtain NIMP (NASONEX) box(es) if needed.
- Download e-diary and review the data; remind patient to bring the device to the next visit.
- Perform blood sampling for serum dupilumab concentration.
- Perform spirometry (for patients with asthma) and record FEV1, FVC and FEF 25-75 result in the e-CRF.
- Measure vital signs (blood pressure, heart rate, respiration rate, body temperature, weight).
- Perform physical examination.
- Perform ECG (refer to [Section 9.4.6](#)).
- Perform CT scan (unless not approved by local ethics committee).
- Perform nasal endoscopy and send to Central Reader.
- Administer smell test (UPSIT).
- Obtain blood samples for (prior to IMP):
  - Hematology (see [Section 9.4.2](#) for details),
  - Serum chemistry (see [Section 9.4.2](#) for details).
- Perform blood sampling for Hepatitis B viral load (for patients in Japan [or other countries/regions if there is local regulatory requirement] who are HBsAg negative and HBsAb positive at V1).
- Perform serum sampling for ADA.
- Obtain serum and plasma for biomarkers, see [Section 9.5.2](#)
- Perform blood sampling for stored serum for those patients who have signed a specific informed consent form.
- Perform blood sampling for total IgE.

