2.4.4.1 Analysis of primary efficacy endpoint(s)

Co-primary efficacy variables

The co-primary efficacy variables are: change from baseline in NC and in NPS (change from baseline in NC, NPS and LMK for Japan) at Week 24 assessed for dupilumab 300 mg q2w (pooled A and B arms) versus placebo, respectively.

The following null hypothesis and alternative will be tested for pooled dupilumab arms against placebo:

- H0: No treatment difference between the dupilumab dose regimen and placebo.
- H1: There is a treatment difference between the dupilumab dose regimen and placebo

Primary statistical model (ITT analysis)

Each of the 2 co-primary efficacy endpoints (3 co-primary efficacy endpoints for Japan) will be analyzed using a hybrid method of the worst-observation carried forward (WOCF) and multiple imputation. Data collected after treatment discontinuation will be included in the analysis. With this approach, for patients who undergo surgery for NP or receive SCS for any reason, data collected postsurgery (actual date) or post SCS will be set to missing, and the worst postbaseline value on or before the time of surgery or SCS will be used to impute missing Week 24 value (for patients whose postbaseline values are all missing, the baseline will be used to impute). For patients who discontinue the treatment without being rescued by surgery or receiving SCS, a multiple imputation approach will be used to impute missing Week 24 value, and this multiple imputation will use all patients who have not been rescued by surgery or receiving SCS at Week 24. Each of the imputed complete data will be analyzed by fitting an ANCOVA model with the baseline value of the corresponding co-primary endpoint, treatment group, asthma/NERD status, prior surgery history, and regions as covariates. Statistical inference obtained from all imputed data will be combined using Rubin's rule. Descriptive statistics including number of patients, mean, standard error, and least squares (LS) means will be provided. In addition, difference in LS means and the corresponding 95% confidence intervals (CI) will be provided along with the p-values.

Imputation and analysis model will be built with the following sample SAS code:

1. 40 datasets with a monotone missing pattern will be obtained, induced by Markov Chain Monte Carlo (MCMC) method on patients who have not been rescued by surgery or receiving SCS at Week 24.

```
proc mi data=dat_etd seed=14280 nimpute=40 out=dat_mc;  

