2.4.4.3 Multiplicity issues

The multiplicity procedure is proposed to control the overall type-I error rate for testing the co-primary and selected secondary endpoints. The overall alpha is 0.05. The comparisons with placebo will be tested based on the hierarchical order below at 2-sided $\alpha = 0.05$:

1) Co-primary efficacy endpoints:

In countries other than Japan:

- Change from baseline in NC and in NPS at Week 24 for 300mg q2w versus placebo.

[figure not shown]
In Japan:

- Change from baseline in NC, in NPS, and in CT LMK at Week 24 for 300mg q2w versus placebo.

2) Secondary efficacy endpoints:

- Change from baseline in CT LMK score at Week 24 for 300mg q2w versus placebo (this will not be a secondary endpoint for Japan as it is already a co-primary endpoint).
- Change from baseline in TSS at Week 24 for 300mg q2w versus placebo.
- Change from baseline in UPSIT at Week 24 for 300mg q2w versus placebo.
- Change from baseline in loss of smell daily symptoms at Week 24 for 300mg q2w versus placebo.
- Change from baseline in SNOT-22 at Week 24 for 300mg q2w versus placebo.
- Change from baseline in NPS at Week 52 for q2w (Arm A) versus placebo (Arm C).
- Change from baseline in NC at Week 52 for q2w (Arm A) versus placebo (Arm C).
- Change from baseline in SNOT-22 at Week 52 for q2w (Arm A) versus placebo (Arm C).
- Proportion of patients requiring rescue treatment defined as: use SCS or NP surgery (actual or planned) during the treatment period for 300mg q2w versus placebo using the pooled data from the EFC14280 and EFC14146.[†]
- Change from baseline in FEV1(L) at Week 24 for 300mg q2w versus placebo for patients with co-morbid asthma using the pooled data from the EFC14280 and EFC14146.*

The figure below shows hierarchies for individual studies of EFC14280 and EFC14146 as well as the pre-specified pooled analysis for proportion of patients requiring rescue treatment with SCS or NP surgery and change from baseline in FEV1(L) at Week 24.

†: The pooled analysis for this endpoint (Proportion of patients requiring rescue treatment with SCS or NP surgery) will be tested in the hierarchy only when in both EFC14280 and EFC14146 hierarchies, all endpoints before this one reach statistical significance with p -value ≤ 0.05 .

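### After the early-termination visit Protocol 10.3.1 schedules no UPSIT or spirometry, so unrescued patients seen at that visit before Day 141 have no planned Week 24 value for two endpoints in the hierarchy

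*Protocol*

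**What the plan says.** **Return visits.** Protocol 10.3.1 asks patients who stop permanently to "Return to the study site for evaluations of NPS, SNOT-22, at" weeks that depend on when the early-termination (ETD) visit took place: "Week 24, Week 52: If the ETD visit occurred between Week 0-Week 16", and "Week 52: If the ETD visit occurred between >Week 16-Week 40". Separately, it asks for CT at Weeks 24 and 52 whatever the date of stopping, for PK and ADA sampling, and for continued e-diary entries on congestion, smell and rhinorrhea. UPSIT and spirometry are not on the list.

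**ETD visit.** Under the same section, patients are "assessed as soon as possible using all procedures normally planned for the End-of-treatment Visit with the exception of CT Scan". That visit's list (Protocol 10.1.14) includes "Administer smell test (UPSIT)" and, for patients with asthma, spirometry.

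**Synopsis.** The post-treatment paragraph, which also covers early discontinuation, has patients return for evaluations that include the "University of Pennsylvania Smell Identification Test (UPSIT), NPS, PROs (SNOT-22, VAS"), and refers to 10.3.1 for details.

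**Analysis.** The hierarchy in SAP 2.4.4.3 contains "Change from baseline in UPSIT at Week 24 for 300mg q2w versus placebo" and ends with Week 24 FEV1 in asthma patients, pooled with EFC14146. SAP 2.4.4.2 gives both endpoints the same hybrid WOCF and multiple-imputation handling as the co-primaries. For that approach SAP 2.4.4.1 says: "Data collected after treatment discontinuation will be included in the analysis".

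**The concern.** The analysis is meant to use what happens to patients after they stop treatment. For the other Week 24 endpoints in the hierarchy, 10.3.1 arranges some collection after the ETD visit. For UPSIT and FEV1 it arranges none, so the missing Week 24 values fall to the imputation model.

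That model (sample code in SAP 2.4.4.1) contains strata, region, treatment arm, baseline and changes at earlier visits. It has no indicator for having stopped. It is fitted on all unrescued patients, most of whom should still be on drug at Week 24. If stopping changes the course of smell or lung function, the model has little information from which to learn it. The sensitivity analyses that would test this (copy increment from placebo, tipping point) are specified in SAP 2.4.4.1 for the co-primaries only. Protocol 11.4.2.6 promises sensitivity analyses in general terms, but the SAP specifies none for UPSIT or FEV1.

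For UPSIT the protocol also disagrees with itself, so sites may handle these patients differently.

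**Working it through.** **1. Planned Week 24 collection after stopping, by hierarchy endpoint**

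| Endpoint | Source after the ETD visit (Protocol 10.3.1) |
|---|---|
| NC, TSS, loss of smell | e-diary continues |
| NPS, SNOT-22 | Week 24 return, if the ETD visit was in Weeks 0-16 |
| LMK | CT at Week 24 |
| UPSIT | none in 10.3.1; named in the synopsis |
| FEV1 (asthma) | none in 10.3.1 or the synopsis |

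The synopsis entry cannot mean the Week 64 visit, because neither the flow chart (1.2) nor Visit 11 (10.1.15) has UPSIT there. Protocol 10.3.4 has a general rule to follow study procedures to the scheduled end, but it too refers to 10.3.1 for the assessments.

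**2. When the ETD value counts as Week 24**

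In SAP Table 4 the Week 24 window is Days 141-266 for UPSIT and Days 141-224 for spirometry. An ETD value before Day 141 falls in an earlier window. There it can inform the imputation, unless another value in that window lies closer to the target day (SAP 2.5.4).

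**3. How many patients this could affect (illustration)**

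The plan states no figure on this point. Its planning figures are 25% dropout and 240 versus 120 patients (Protocol 11.1). They reproduce the stated 99% power for the co-primaries. With 180 versus 90 patients, power = Φ(ES/√(1/180 + 1/90) − 1.96), which gives Φ(4.14 − 1.96) = 98.5% for NC (ES 0.534) and Φ(4.55 − 1.96) = 99.5% for NPS (ES 0.588). No UPSIT effect size or SD is given, so the stated power above 99% for UPSIT cannot be checked.

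Assumptions made here: stopping days are even over Days 1-168, and the ETD visit follows 0 to 14 days later.

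- ETD visit on the day of stopping: stops on Days 141-168 are in the window, 28/168 = 17%.
- ETD visit 14 days later: stops on Days 127-168 are in the window, 42/168 = 25%.
- So 75 to 83% of those who stop before Week 24 have no planned Week 24 value.

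Number stopping before Week 24, out of 360:

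- all dropout before Week 24: 0.25 × 360 = 90;
- dropout even over 52 weeks: 90 × 24/52 = 41.5.

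UPSIT values missing at Week 24:

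- 90 × 0.833 = 75, or 90 × 0.75 = 67.5;
- 41.5 × 0.833 = 34.6, or 41.5 × 0.75 = 31.2.

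The range is 31 to 75 patients, or 31.2/360 = 9% to 75/360 = 21%. Each count treats every dropout as an unrescued stopper, so it is a ceiling for its scenario. FEV1 counts are smaller because only asthma patients contribute.

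**4. What adding the tests would change**

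If they were added only where NPS and SNOT-22 are already due at Week 24 (ETD visit by Week 16, Day 113), patients with an ETD visit on Days 114-140 would still be missed. That is 27/168 = 16%, or about 14 of 90 (7 of 41.5). Planned coverage would rise from 17-25% to 84%. Patients in the Day 114-140 gap are already due at Week 24 for CT, so using that visit would close it.

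**The case against.** The strongest reply is that these patients are not unobserved. The ETD visit includes UPSIT and, in asthma patients, spirometry. From Day 141 that value is the Week 24 value. Before then it can enter as an earlier visit, and the imputation conditions on earlier visits, so a patient who was doing poorly is not simply given the arm's mean. This stands. A reader might infer that UPSIT and FEV1 have no off-treatment data at all, and the documents do not support that.

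Second, Protocol 4.4.2 reports from the phase 2 study that improvement over baseline persisted through 16 weeks off drug. If that holds here, imputing from patients on treatment may do little harm. This also stands, although under the present schedule the persistence would go largely unmeasured for UPSIT.

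Third, the SAP sentence on data after discontinuation says how collected data are used. It does not promise that every endpoint is collected, so it is not contradicted. Nor do NPS and SNOT-22 have full cover: they share the gap for ETD visits after Week 16 but before Day 141.

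Fourth, the tested FEV1 result pools EFC14146, whose schedule is not in these documents. The point therefore reaches only this study's share.

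Limiting copy-increment to the co-primaries is a defensible choice in itself. It is less comfortable for the two endpoints with the least data after stopping.

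**Conclusion.** The point holds in a limited form. Section 10.3.1 conflicts with the synopsis on UPSIT and provides no spirometry after the ETD visit. Unrescued patients whose ETD visit falls before Day 141 therefore have no planned Week 24 value for UPSIT or, in this study's part, for FEV1. Both endpoints are in the hierarchy and would be imputed for these patients without a term for stopping and without a specified sensitivity analysis.

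The count of 31 to 75 patients for UPSIT rests on the assumptions shown. It falls if some of them are rescued, since they then go to WOCF. Patients who leave the study would not attend an added visit either. I have read the ETD visit as a scheduled measurement for SAP Table 4, which the SAP does not say outright.

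A reader might multiply the 25% dropout by an assumed loss of effect and call the product the bias. That would place all dropout before Day 141 and treat it as unrescued. It would also ignore the conditioning on earlier visits and set aside the persistence described in Protocol 4.4.2. The size of any bias cannot be derived from the documents. This is a cheap improvement to two key secondary endpoints and does not affect the co-primary results.

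**What to change.** - **Protocol:** reconcile the synopsis and 10.3.1 by adding UPSIT to the 10.3.1 return visits at Week 24 and Week 52. Make the Week 24 UPSIT apply also to patients with early termination after Week 16 but before Day 141, who are already asked back then for CT. Name it separately from the CT, because some countries are exempt from study CT pending approval.
- **Where feasible:** add spirometry for patients with asthma at the same visits.
- **SAP:** extend the planned copy-increment analysis to Week 24 UPSIT and FEV1.

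The cost is a booklet of about 15 minutes (Protocol 9.2.1.2), spirometry in asthma patients at visits largely already planned, and one repeat of a specified analysis. Values not collected at Week 24 cannot be recovered later.

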### **10.3.2 Temporary treatment discontinuation with investigational medicinal product(s)**

Temporary treatment discontinuation may be considered by the Investigator because of AEs. Re-initiation of treatment with the IMP will be made under close and appropriate clinical/and or laboratory monitoring once the Investigator will have considered according to his/her best medical judgment that the AE is sufficiently resolved and unlikely to recur after resuming therapy with IMP.

In addition, any of the following conditions will be a cause for temporary treatment discontinuation:

- Infections or infestations that do not respond to medical treatment should have study drug discontinued until the infection is resolved
- Any laboratory abnormality that meets temporary treatment discontinuation criteria as per [Appendix G](#).

For all temporary treatment discontinuations, duration should be recorded by the Investigator in the appropriate pages of the e-CRF. If the IMP is interrupted for more than 2 doses, then the patient should permanently discontinue the study treatment.

### 10.3.3 List of criteria for permanent treatment discontinuation

The patients may withdraw from treatment with the IMP if they decide to do so, at any time and irrespective of the reason, or this may be the Investigator's decision. All efforts should be made to document the reasons for treatment discontinuation and this should be documented in the e-CRF.

Patients must be withdrawn from the study (ie, from any further IMP or study procedure) for the following reasons:

- At their own request or at the request of their legally authorized representative (legally authorized representative means an individual or judicial or other body authorized under applicable law to consent on behalf of a prospective patient to the patient's participation in the procedure(s) involved in the research).
- If, in the Investigator's opinion, continuation in the study would be detrimental to the patient's well-being.

In case of surgery for NP (refer to [Section 9.2.1.5](#) for details).

- At the specific request of the Sponsor.
- In the event of a critical protocol deviation, at the request of the Investigator or the Sponsor.
- Any code broken requested by the Investigator will lead to permanent treatment discontinuation.
- In the event of an anaphylactic systemic allergic reaction that is related to IMP and that requires treatment.
- In the event that the patient is diagnosed with a malignancy during the study, excluding carcinoma in situ of the cervix or squamous or basal cell.
- Pregnancy.
- Any opportunistic infection, such as tuberculosis or other infections whose nature or course may suggest an immunocompromised status (refer to [Appendix I](#)).
- Serum ALT >3 ULN and total bilirubin >2ULN.
- Serum ALT >5 ULN if baseline ALT <2 ULN or ALT >8 ULN if baseline ALT >2 ULN.

Stopping rules described in [Appendix G](#) should be applied.

